Follow-up AML Therapies		X	All discontinued participants, regardless of reason for discontinuation, should be followed for AML therapies every 4 weeks (\pm 3 days) for the first year and then every 12 weeks (\pm 14 days) until death, loss to follow-up, withdrawal of consent from further follow-up, or end of study.

Table 2-3: End-of-treatment and Follow-up Procedural Outline (CA055005)

Procedure	End of Treatment /Early Termination	Follow-up	Notes
Survival Follow-up		X	All discontinued participants, regardless of reason for discontinuation, should be followed for survival every 4 weeks (\pm 3 days) for the first year and then every 12 weeks (\pm 14 days) until death, lost to follow-up, withdrawal of consent from further follow-up, or the end of the study. The survival follow-up can be performed via a telephone interview.
Health Outcomes Assessments			
FACIT-Fatigue Scale and EQ-5D-5L	X		Each assessment should be completed at the start of the clinic visit prior to dosing and other study assessments. See Section 9.1.2 .

Abbreviations: ALT, alanine aminotransferase; AML, acute myeloid leukemia; ANC, absolute neutrophil count; AST, aspartate aminotransferase; BUN, blood urea nitrogen; COVID-19, coronavirus disease 2019; CR, complete remission; CRF, case report form; CRi, complete remission with incomplete blood count recovery; EOT, end of treatment; EQ-5D-5L, EuroQol 5-dimension 5-level questionnaire; FACIT, Functional Assessment of Chronic Illness Therapy; IgG, immunoglobulin G; IgM, immunoglobulin M; IP, Investigational Product; IWG, International Working Group; LDH, lactate dehydrogenase; MCH, mean corpuscular hemoglobin; MCHC, mean corpuscular hemoglobin concentration; MCV, mean corpuscular volume; RBC, red blood cell; SAE, serious adverse event; WBC, white blood cell; WOCBP, women of childbearing potential.

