Procedure	During Treatment Cycle 1 Day 1 (1 Cycle = 4 Weeks)	During Treatment Cycle 1 Days 8, 15, and 22 (± 3 Days)	During Treatment Cycle 2 Day 1 (± 3 Days)	During Treatment Cycle 2 Days 8, 15, and 22 (± 3 days)	During Treatment Cycle 3 and beyond Day 1 (± 3 Days)	During Treatment Cycle 3 and beyond Day 15 ^a (± 3 Days)	Notes
							performed only if clinically indicated.
Bone Marrow Biopsy					X		Bone marrow biopsy may be needed to assess bone marrow status if an adequate bone marrow aspirate cannot be attained.
Cytogenetic Testing					X		Bone marrow aspirate sample tube for cytogenetic testing/chromosome analysis to be obtained for evaluation by central laboratory to obtain karyotype. During the study, repeat of bone marrow cytogenetic testing is to be completed whenever a bone marrow aspirate is obtained.
Peripheral Blood Smear					X		Whenever bone marrow aspirate (or biopsy) slides are sent to the central reviewer, a peripheral blood smear slide should also be submitted.
IWG Response Assessment					X		International Working Group (IWG) response assessment will be done at Cycles 3, 6, 9, 12, 15, 18, 21, 24, 30, and 36. After Cycle 36, response assessment for disease relapse will be

Table 2-2: On-treatment Procedural Outline (CA055005)

Procedure	During Treatment Cycle 1 Day1 (1 Cycle = 4 Weeks)	During Treatment Cycle 1 Days 8, 15, and 22 (± 3 Days)	During Treatment Cycle 2 Day 1 (± 3 Days)	During Treatment Cycle 2 Days 8, 15, and 22 (± 3 days)	During Treatment Cycle 3 and beyond Day 1 (± 3 Days)	During Treatment Cycle 3 and beyond Day 15 ^a (± 3 Days)	Notes
							performed only if clinically indicated. Participants should be assessed for CR/CRi status maintenance, relapse after CR/CRi, or disease relapse.
Health Outcomes Assessments							
FACIT-Fatigue Scale and EQ-5D-5L	X		X		X		Each assessment should be completed at the start of the clinic visit prior to dosing and other study assessments. See Section 9.1.2 .
Study Intervention							
Dispense/Administer	X		X		X		IP is scheduled to be taken for 1-14 days of each cycle, unless there has been a schedule modification from 14 days to 7 days of IP administration due to toxicity. Participants with ≥5% to ≤15% blasts in the bone marrow or peripheral blood response assessment may receive 200mg of IP for the first 21 days per cycle.
Provide/Collect Medication Diary	X		X		X		

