5 STUDY DESIGN

5.1 Overall Design

This is a multicenter, placebo-controlled, Phase 2 study with a double-blind, randomized, 2:1 group design in Japanese participants with de novo AML or AML secondary to prior diagnosis of MDS or CMML, aged ≥ 55 years, who are in first CR/CRi following induction therapy with or without consolidation chemotherapy.

The study consists of 3 phases; the Screening Phase, the Treatment Phase, and the Follow-up Phase. The study design schematic is presented in [Figure 5.1-1](#).

Approximately 15 participants will be randomized 2:1 to CC-486 or placebo.

- Approximately 10 participants will receive CC-486.
- Approximately 5 participants will receive placebo.

After informed consent is obtained, participants will undergo screening procedures to determine eligibility (28 days for screening). Eligible participants will be dynamically randomized using an Interactive Response Technology (IRT) by the following factors:

1. Age: 55 to 64 years/ \geq 65 years
2. Prior history of MDS/CMML: Yes/No
3. Cytogenetic risk: Intermediate/Poor
4. Consolidation therapy: Yes/No

Randomization must occur within 4 months (\pm 7 days) of achieving the first CR/CRI.

After randomization, no crossover between the treatment arms will be permitted at any point during the study. During the Double-blind Treatment Phase, participants will ingest Investigational Product (IP) (CC-486 tablets or placebo tablets) for the first 14 days of each 28-day cycle. Dose modifications may occur for managing toxicity if necessary during treatment ([Section 7.4.1](#)).

During the Double-blind Treatment Phase, participants will be assessed for safety, tolerability, and efficacy. Assessments during the Double-blind Treatment Phase will include monitoring for AEs, monitoring for relapse of AML, physical examination, vital signs and weight measurement, Eastern Cooperative Oncology Group (ECOG) performance status, hematology and serum chemistry, pregnancy testing (women of childbearing potential [WOCBP] only), concomitant medications, therapies and procedures, review of bone marrow aspirate (or biopsy if adequate aspirate is not attainable) and peripheral blood smear slides, cytogenetic analysis, CR/CRI status assessment, bone marrow and peripheral blood sampling for biomarker analysis, blood sampling for PK analysis, IP administration and accountability, and HRQoL.

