7.4 Dosage Modification

7.4.1 Dose Modifications for Toxicity

Participants should be monitored for toxicity using the National Cancer Institute Common Terminology Criteria for Adverse Events (NCI-CTCAE), Version 5.0, as a guide for the grading of severity.

If a certain level of toxicity is observed and considered by the investigator to be at least possibly related to treatment, IP dosing may be interrupted, delayed, or modified. The Investigator is encouraged to contact the Medical Monitor prior to any treatment adjustment.

A maximum of one dose reduction to a daily dose of 150 mg is permitted in the event of toxicity. If toxicity persists, a maximum of one treatment schedule modification from 14 to 7 days (21 days to 14 days for those participants whose dose schedule has been extended due to disease progression) is permitted in the event of continuing toxicity that does not respond to dose reduction. The decision to modify a participant's treatment schedule from 14 to 7 days (21 days to 14 days for those participants whose dose schedule has been extended due to disease progression) should first be discussed with the Medical Monitor or designee. Participants should not receive less than 150 mg IP or be scheduled to receive treatment for less than 7 days.

Participants who have their IP dose reduced or treatment schedule modified may return to their original dose and/or schedule in a step-wise fashion upon discussion and agreement between the investigator and the Medical Monitor provided that the increased dose or treatment schedule is tolerable and at least two additional treatment cycles have occurred since the dose reduction or treatment schedule modification. The treatment schedule should first be increased from 7 to 14 days, followed by a dose escalation step from 150 to 200 mg.

Dose Modification for Febrile Neutropenia \geq Grade 3

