7.4.2 Dose and Schedule Adjustment in Participants with AML Relapse/Progression

In participants on study who have subsequent evidence of AML relapse with blasts $\geq 5\%$, either in the peripheral blood count or bone marrow, and provided the blasts are no greater than 15% in the blood or bone marrow, escalation of the dosing regimen (dose and/or schedule) can be implemented as follows (provided it is in the best interest to do so as judged by the Investigator):

- Participant currently on blinded treatment of CC-486 200 mg or placebo QD for 14 days — escalate schedule to CC-486 200 mg or placebo QD for 21 days
- Participant currently on blinded treatment of CC-486 150 mg or placebo QD for 14 days — escalate dose schedule, as a first step, to CC-486 150 mg or placebo QD for 21 days and then escalate dose to CC-486 200 mg or placebo QD for 21 days

- Participant currently on blinded treatment for CC-486 150 mg or placebo QD for 7 days - escalate dose schedule, as a first step, to CC-486 150 mg or placebo QD for 14 days and then escalate dose to CC-486 200 mg or placebo QD for 14 days

In cases where relapse is noted within a week of starting the next cycle, and there is a desire to escalate the dose schedule during the cycle, contact the Medical Monitor to discuss this, in order to obtain the additional required IP.

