9 STUDY ASSESSMENTS AND PROCEDURES

- Study procedures and timing are summarized in the Schedule of Activities.
- Protocol waivers or exemptions are not allowed.
- All immediate safety concerns must be discussed with the Sponsor immediately upon occurrence or awareness to determine if the participant should continue or discontinue treatment.
- Adherence to the study design requirements, including those specified in the Schedule of Activities, is essential and required for study conduct.
- All screening evaluations must be completed and reviewed to confirm that potential participants meet all eligibility criteria before randomization. The investigator will maintain a screening log to record details of all participants screened and to confirm eligibility or record reasons for screening failure, as applicable.

- Procedures conducted as part of the participant's routine clinical management (eg, blood count) and obtained before signing of informed consent may be utilized for screening or baseline purposes provided the procedure meets the protocol-defined criteria and has been performed within the time frame defined in the Schedule of Activities.
- Safety/laboratory/analyte results that could unblind the study will not be reported to investigative sites or other blinded personnel until the study has been unblinded.

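### At 5–15% blasts, the Table 2-2 dosing note omits the current-dose steps of Section 7.4.2 for toxicity-reduced participants; a smaller mismatch affects the renal row of Table 7.4.1-1

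*Combined protocol and SAP*

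**What the plan says.** **Escalation at 5–15% blasts.** The Dispense/Administer note in Table 2-2 states that these participants "may receive 200mg of IP for the first 21 days per cycle". It sets no condition on current dose and does not cite Section 7.4.2.

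Section 7.4.2 covers the same situation but works from the participant's current regimen:

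- On 200 mg for 14 days: "escalate schedule to CC-486 200 mg or placebo QD for 21 days".
- On 150 mg for 14 days: "escalate dose schedule, as a first step, to CC-486 150 mg or placebo QD for 21 days". The move to 200 mg for 21 days comes after that.
- On 150 mg for 7 days: "escalate dose schedule, as a first step, to CC-486 150 mg or placebo QD for 14 days", followed by 200 mg for 14 days.

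Escalation under Section 7.4.2 also requires the investigator to judge it to be in the participant's best interest. Section 5.1 refers the reader to Section 7.4.2 for it.

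**Renal toxicity.** Section 7.4.1 gives a general order for toxicity: one dose reduction to 150 mg, and then "If toxicity persists, a maximum of one treatment schedule modification from 14 to 7 days" (21 to 14 days for an extended schedule). Its renal paragraph follows this order. It reduces to 150 mg at the first event, allows a schedule cut if the elevation recurs in the following cycle, and discontinues if the problem continues after that. The renal row of Table 7.4.1-1 has the reduction to 150 mg and then discontinuation, with no schedule cut between them.

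**The concern.** Both mismatches fall on participants who have already had a toxicity reduction, for whom the size of the next dosing step matters most. A site dosing from the Table 2-2 note alone could take a reduced participant to the highest regimen in the protocol in one move, where Section 7.4.2 calls for a smaller step first. A site using the renal row alone would stop a participant whom the text would allow to continue on a shorter schedule.

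What is at stake is individual safety and exposure, and, for the renal rule, time to discontinuation from treatment, which is a secondary endpoint. The risk assessment in Section 3.3.1 relies on a detailed look at efficacy and safety in individual participants, so a single divergent dosing decision would be visible in a study of about 15.

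**Working it through.** The protocol gives no figure to reproduce here. The check sets the paired rules side by side and converts each regimen to milligrams per 28-day cycle.

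**Formula.** mg per cycle = daily dose × dosing days.

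| Regimen | Calculation | mg per cycle |
|---|---|---|
| 150 mg, 7 days | 150 × 7 | 1,050 |
| 150 mg, 14 days | 150 × 14 | 2,100 |
| 200 mg, 14 days | 200 × 14 | 2,800 |
| 150 mg, 21 days | 150 × 21 | 3,150 |
| 200 mg, 21 days | 200 × 21 | 4,200 |

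**Escalation at 5–15% blasts: Table 2-2 note against the first step in Section 7.4.2**

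| Current regimen | Table 2-2 note | 7.4.2 first step | Difference |
|---|---|---|---|
| 200 mg × 14 (2,800) | 4,200 (4,200/2,800 = 1.5-fold) | 4,200 (1.5-fold) | 0 |
| 150 mg × 14 (2,100) | 4,200 (4,200/2,100 = 2-fold) | 3,150 (3,150/2,100 = 1.5-fold) | 4,200 − 3,150 = 1,050 |
| 150 mg × 7 (1,050) | 4,200 (4,200/1,050 = 4-fold) | 2,100 (2,100/1,050 = 2-fold) | 4,200 − 2,100 = 2,100 |

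So there is no conflict for an unreduced participant. From 150 mg × 14, the note allows 4,200/3,150 = 1.33 times the first step in Section 7.4.2. From 150 mg × 7, it allows 4,200/2,100 = 2 times that step.

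**Does the note exclude reduced participants?** It does not do so expressly. The sentence just before it in the same cell mentions participants cut from 14 to 7 days for toxicity, so reduced schedules were in view, and the blast sentence does not set them apart. A schema footnote limits something to participants on the initially assigned dose and schedule. Its anchor is in a figure that is not shown, and it is not attached to Table 2-2.

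**Which order fits the rest of the protocol?** The stepped one. For participants recovering from toxicity, Section 7.4.1 allows return to the starting regimen only in steps, with schedule before dose, after at least two further cycles and with Medical Monitor agreement. That rule addresses a different situation, but it points the same way as Section 7.4.2.

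**Renal toxicity, first recurrence after reduction to 150 mg**

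| Current regimen | 7.4.1 text (optional cut) | Table 7.4.1-1 renal row |
|---|---|---|
| 150 mg × 14 | 150 × 7 = 1,050 mg | stop, 0 mg |
| 150 mg × 21 | 150 × 14 = 2,100 mg | stop, 0 mg |

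**Reach.** Section 5.1 states: "Approximately 10 participants will receive CC-486". The other 5 or so receive placebo, where neither difference carries azacitidine exposure. The protocol gives no rate for either situation, so the number affected cannot be calculated.

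**The case against.** The strongest reply is that the detailed text already settles the matter. The Table 2-2 sentence sits in the notes column of a procedural outline, says only what a participant may receive, and never mentions the 150 mg level. It reads naturally as shorthand for the default regimen. Section 5.1 sends the reader to Section 7.4.2, and a site that follows Section 7.4.2 breaches nothing in the note. This largely stands, and it is why the point is minor. It does not remove the mismatch: the note is not limited to unreduced participants, it gives no cross-reference, and nothing in the protocol says which source prevails.

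On the renal rule, the schedule cut in the text is optional, so a site that discontinues under the table does not contravene the text. That also stands. The difference is that the table leaves out an option, not that it orders something the text forbids.

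Three stronger readings are tempting but not supported:

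- *The note is binding.* Section 9 says: "Adherence to the study design requirements, including those specified in the Schedule of Activities, is essential and required for study conduct". That sentence concerns requirements, and a permission is not a requirement, so it does not give the note precedence over Section 7.4.2.
- *The ceilings differ from 150 mg × 7.* The listed path there ends with "then escalate dose to CC-486 200 mg or placebo QD for 14 days", which might suggest that 21 days can never be reached. But the rules in Section 7.4.2 are keyed to the current regimen, and a participant who reaches 200 mg × 14 then fits the rule for that regimen. The section does not say whether that further step is excluded, so only the first-step difference is established.
- *The renal row has visibly lost a line.* The row carries a remark about discussing schedule changes with the Medical Monitor. The nausea/vomiting row carries the same remark and also has no schedule step, so the remark is not reliable evidence. The general order in Section 7.4.1 is the better ground for aligning the row.

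**Conclusion.** The inconsistency is real and is in current operative text. For toxicity-reduced participants with 5–15% blasts, the Table 2-2 note skips the first step that Section 7.4.2 sets: 4,200 against 3,150 mg per cycle from 150 mg × 14, and 4,200 against 2,100 mg from 150 mg × 7. For participants on 200 mg × 14 there is no conflict. The renal mismatch is secondary, because it concerns an optional step.

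This is a minor internal inconsistency with safety relevance, not a questionable design choice. The per-cycle figures assume that every dosing day is taken as prescribed; no interval between escalation steps is assumed. The blast mismatch matters only if several things coincide: active treatment, an earlier toxicity reduction, blasts in the 5–15% range, a decision to escalate, and a site working from the note alone. The number affected is therefore likely to be a few at most.

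A reader might infer that the primary analysis is compromised. The documents do not support that: Section 10.4.2 defines relapse for RFS by IWG criteria on central review, so the definition does not depend on which dosing rule is followed. A reader might also take the account in Section 5.5 of Japanese MDS participants stopping 300 mg × 21 days as evidence of harm at 200 mg × 21 days. It came from a higher dose in a different disease and does not show that.

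**What to change.** In Table 2-2, replace the blast sentence with: *For participants with 5% to 15% blasts, escalate according to current dose and schedule as in Section 7.4.2.*

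In the renal row of Table 7.4.1-1, add the optional 14-to-7-day (21-to-14-day) schedule cut at first recurrence on 150 mg, before the discontinuation step. This matches the renal paragraph and the general dose-then-schedule order in Section 7.4.1. If the sponsor intends the stricter rule, delete the schedule cut from the renal paragraph instead.

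The cost is one sentence and one table line in the next amendment, with no added procedures or participants.

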3 INTRODUCTION

This is a Phase 2, randomized, double-blind, placebo-controlled study to compare the efficacy and safety of CC-486 plus best supportive care versus best supportive care as maintenance therapy in Japanese participants with acute myeloid leukemia (AML) in complete remission. The primary objective of the study is to evaluate whether maintenance therapy with CC-486 improves relapse-free survival (RFS) compared with placebo in Japanese participants ≥ 55 years with AML, who have achieved first complete remission (CR) or complete remission with incomplete blood count recovery (CRi) after induction with intensive chemotherapy with or without consolidation chemotherapy. Participants will be randomized 2:1 to receive 200 mg CC-486 once daily (QD) or placebo for the first 14 days of each 28-day treatment cycle.

A detailed description of the chemistry, pharmacology, efficacy, and safety of CC-486 is provided in the Investigator's Brochure (IB).

3.1 Study Rationale

The standard treatment modality for acute myeloid leukemia (AML) is chemotherapy globally as well as in Japan. The therapeutic approaches are usually divided into two phases: induction of remission and post-remission (consolidation) therapy. A common induction regimen consists of cytarabine 100 mg/m²/day for 7 days combined with daunorubicin 60 to 90 mg/m²/day for 3 days, often referred to as the "7+3 protocol." For post-remission chemotherapy, the same chemotherapy agent used for remission induction is often repeated for one or more cycles, referred to as consolidation chemotherapy. When several courses of consolidation are given, despite achieving complete remission (CR), approximately 50% of younger (< 60 years) and 80% to 90% of older (≥ 65 years) patients will relapse; most of these patients will die due to AML, with median survival from 3 to 12 months after relapse. For patients with relapsed AML, the duration of first CR is strongly correlated with subsequent outcomes, with longer duration of first CR associated with better survival. Therefore, an unmet medical need exists for maintaining a deeper level of remission over a longer duration in patients who achieve remission. Effective maintenance therapy for patients who attain remission with intensive chemotherapy may play a role in preventing relapse and prolonging overall survival (OS), especially in those ineligible for allogeneic hematopoietic stem cell transplantation (HSCT).

CC-486 was confirmed to show statistically significant prolongation of OS and relapse-free survival (RFS) in the maintenance setting in patients ≥ 55 years with AML and in CR or complete remission with incomplete blood count recovery (CRi) after conventional induction chemotherapy with or without consolidation chemotherapy in Study CC-486-AML-001. CC-486 was already approved for the treatment of AML in the United States (US) in September 2020, in Canada in January 2021, and the European Union in June 2021. CC-486 is recommended for as maintenance therapy for patients with AML in complete remission, regardless of age (<60 or ≥ 60 years), in the National Comprehensive Cancer Network (NCCN) Clinical Practice Guideline (Category 2B).²

CA055-005 is a bridging study to provide clinical data that will allow extrapolation of the CC-486-AML-001 study data to Japan. This study is designed as a 2:1 randomization of CC-486 or placebo to assess the efficacy and safety of maintenance treatment with oral azacitidine in a cohort

of Japanese participants \geq 55 years with AML and in CR/CRi after conventional induction chemotherapy with or without consolidation chemotherapy. The primary endpoint is RFS because CC-486-AML-001 has successfully shown survival benefit for not only OS but RFS when compared with best supportive care (BSC). The CC-486 dose that has demonstrated tolerability and shown signs of clinical activity in the ORACLE Study is 200 mg. The primary endpoint of RFS and secondary endpoints of OS, time to relapse from CR/CRi, time to discontinuation from treatment, safety, pharmacokinetics (PK), and health-related quality-of-life (HRQoL) will be evaluated and allow for a comprehensive investigation of efficacy, exposure/safety, and HRQoL appropriateness of the clinical recommended dose for the Japanese population in comparison with the data from the Study CC-486-AML-001.

